9.7.4 Interim analysis

There will be interim analyses according to Korean regulations, see section 6.

9.7.5 Handling of missing data

Maximum attempt will be made to ensure the completeness of data collection. All available data will be used in the data analysis. Missing or incomplete dates of AEs are imputed according to BI standard.

9.8 QUALITY CONTROL

The quality control, review, and monitoring plan are summarized below. Greater details are documented in the DMP and PMP.

All entries in eCRFs and the existing coding will be stored in a database. The structure of the database is based on the division into sections and entry fields defined in the eCRFs. To improve and ensure data quality, data checks will be performed automatically in the eCRFs directly on electronic entry at the study site.

Plausible value ranges for numerical data entries and logical data and list entries will be filed in the eCRFs. The tests for consistency and completeness based on this will be performed during entry in the eCRFs. The validity of the recorded data will therefore be ensured by the

ONIS New Data Collection Protocol

Page 24 of 54

Study number: 1245-0323 Document number: c42645766-03

Proprietary confidential information © 2024 Boehringer Ingelheim International GmbH or one or more of its affiliated companies

validations incorporated in the documentation system, which highlight incorrect or implausible entries to the data entry clerk/doctor.

All changes after initial data entry will be documented in an audit trail. An additional inspection/quality assurance check of the data collected within this ONIS can be performed in case of any deviation.

9.9 LIMITATIONS OF THE RESEARCH METHODS

9.9.1 Loss to follow-up

All efforts will be made to minimize loss to follow-up, particularly in the tracking of lost participants. To the extent possible, occurrence of adverse event, at minimum, for participants lost to follow up will be obtained via pariticipant visit / telephone / letter / email etc. This allows assessing the impact of informative censoring due to treatment discontinuation. Also, participants lost to follow-up will be characterized compared to the remaining participants and reason and time point of loss to follow-up will be evaluated.

9.9.2 Channeling Bias

Channeling bias can occur due to access to product depending on reimbursement circumstances or preferential prescribing in relation to different risks for the events of interest: e.g., a higher frequency of outcome events would be expected in the JARDIANCE® group if JARDIANCE® was prescribed more frequently to high-risk participants compared to other treatments. However, this will not be assessed since there is no comparator group.

9.9.3 Confounding

As in any observational study, confounding may affect the estimation of association between drug exposure and outcome of interest and statistical techniques. When the investigators assess the overall efficacy, different assessment criteria among them may affect the study outcome. Also, information bias may occur and cause a distortion in the observed association due to a lack of accurate measurements of key study variables. If key study variables (exposure, health outcome, or confounders) are inaccurately measured or classified (which may happen in real-world clinical settings), bias in the risk ratio, rate ratio, or odds ratio can be produced.

ONIS New Data Collection Protocol

Page 25 of 54

Study number: 1245-0323 Document number: c42645766-03

Proprietary confidential information © 2024 Boehringer Ingelheim International GmbH or one or more of its affiliated companies

9.10 OTHER ASPECTS

The protocol of this regulatory required ONIS will be submitted to MFDS for approval. Also, the protocol will be submitted to Institutional Review Board (IRBs) whenever required or requested by these study sites. This study will be conducted in accordance with the Standards for Re-examination of New Drugs, etc. Inotified by MFDS, the Korean Pharmaceutical Affairs Code (KPAC), Enforcement Regulation of KPAC and other applicable local laws and industry code (including but not limited to the Regulations on Fair Competition in the Trade of Medicines of the Korea Pharmaceutical and Bio-Pharma Manufacturers Association (KPBMA) and the Korean Research-based Pharma Industry Association (KRPIA)).

will submit interim reports during re-examination period, and the study final report to MFDS upon study completion. The interim report for the final year will be substituted with the final report. When required, the interim reports and the final report will be submitted to the IRBs as well.

9.10.1 Data quality assurance

A quality assurance audit / inspection of this study may be conducted by the sponsor or sponsor's designees or by IRBs / Independent Ethics Committee (IECs) or by regulatory authorities. The quality assurance auditor will have access to all medical records, the investigator's study-related files and correspondence, and the informed consent documentation of this study.

9.10.2 Study records

CRFs for individual participants will be provided by the sponsor, either on paper or via remote data capture, if applicable.

9.10.2.1 Source documents

Source documents provide evidence for the existence of the patient and substantiate the integrity of the data collected. Source documents are filed at the investigator's site.

Data entered in eCRFs that are transcribed from source documents must be consistent with the source documents or the discrepancies must be explained. The investigator may need to request previous medical records or transfer records, depending on the study; also current medical records must be available.

For eCRFs all data must be derived from source documents.

ONIS New Data Collection Protocol

Page 26 of 54

Study number: 1245-0323 Document number: c42645766-03

Proprietary confidential information © 2024 Boehringer Ingelheim International GmbH or one or more of its affiliated companies

9.10.2.2 Direct access to source data and documents

The investigator / institution will permit study-related monitoring, audits, IRB / IEC review and regulatory inspection, providing direct access to all related source data / documents. CRFs / eCRFs and all source documents, including progress notes and copies of laboratory and medical test results must be available at all times for review by the sponsor's clinical study monitor, auditor and inspection by health authorities (e.g. US Food and Drug Administration (FDA)). BI study staff and auditor may review all CRFs / eCRFs, and written informed consents. The accuracy of the data will be verified by reviewing the documents described in Section 9.10.2.1.

10. PROTECTION OF HUMAN SUBJECTS

The study will be carried out in compliance with the protocol, the principles laid down in the Declaration of Helsinki, Guidelines for GPP, Guidelines for Good Pharmacovigilance Practices (GVP) and the relevant BI SOPs. Standard medical care (prophylactic, diagnostic and therapeutic procedures) remains the responsibility of the treating physician of the patient.

The investigator should inform the sponsor immediately of any urgent safety measures taken to protect the study subjects against any immediate hazard, and also of any serious breaches of the protocol.

10.1 STUDY APPROVAL, PATIENT INFORMATION, AND INFORMED CONSENT

This ONIS will be initiated only after all required legal documentation has been reviewed and approved by the respective IRB / IEC and Competent Authority (CA) according to national and international regulations. The same applies for the implementation of changes introduced by amendments.

Prior to patient participation in the study, written informed consent must be obtained from each patient (or the patient's legally accepted representative) per GPP and according to the regulatory and legal requirements of the participating country, if applicable.

10.2 STATEMENT OF CONFIDENTIALITY

Individual patient medical information obtained as a result of this study is considered confidential and disclosure to third parties is prohibited with the exceptions noted below. Patient confidentiality will be ensured by using patient identification code numbers.

Treatment data may be given to the patient's personal physician or to other appropriate medical personnel responsible for the patient's welfare. Data generated as a result of the study need to be available for inspection on request by the participating physicians, the sponsor's representatives, by the IRB / IEC and the regulatory authorities.

ONIS New Data Collection Protocol

Decument numbers of 201700 02

Page 27 of 54

Study number: 1245-0323 Document number: c42645766-03

Proprietary confidential information © 2024 Boehringer Ingelheim International GmbH or one or more of its affiliated companies

11. MANAGEMENT AND REPORTING OF ADVERSE EVENTS/ADVERSE REACTIONS

11.1 DEFINITIONS OF ADVERSE EVENTS

Adverse Event

An Adverse Event (AE) is defined as any untoward medical occurrence in a patient or clinical investigation subject administered a medicinal product and which does not necessarily have a causal relationship with this treatment. An AE can therefore be any unfavorable and unintended sign (e.g. an abnormal laboratory finding), symptom, or disease temporally associated with the use of a medicinal product, whether or not considered related to the medicinal product.

Adverse Drug Reaction

An Adverse Drug Reaction (ADR) is defined as a response to a medicinal product which is noxious and unintended. Response in this context means that a causal relationship between a medicinal product and an AE is at least a reasonable possibility. Adverse reactions may arise from use of the product within or outside the terms of the marketing authorization or from occupational exposure. Conditions of use outside the marketing authorization include off-label use, overdose, misuse, abuse and medication errors.

Serious Adverse Event

A Serious Adverse Event (SAE) is defined as any AE which

- results in death,
- is life-threatening,
- requires in-patient hospitalization, or
- prolongation of existing hospitalization,
- results in persistent or significant disability or incapacity, or
- is a congenital anomaly / birth defect

Life-threatening in this context refers to a reaction in which the patient was at risk of death at the time of the reaction; it does not refer to a reaction that hypothetically might have caused death if more severe.

Medical and scientific judgement should be exercised in deciding whether other situations should be considered serious reactions, such as important medical events that might not be immediately life threatening or result in death or hospitalization but might jeopardize the patient or might require intervention to prevent one of the other outcomes listed above. Examples of such events are intensive treatment in an emergency room or at home for allergic bronchospasm, blood dyscrasias or convulsions that do not result in hospitalization or development of dependency or abuse. Any suspected transmission via a medicinal product of an infectious agent is also considered a serious adverse reaction.

ONIS New Data Collection Protocol

Page 28 of 54

Study number: 1245-0323 Document number: c42645766-03

Proprietary confidential information © 2024 Boehringer Ingelheim International GmbH or one or more of its affiliated companies

Adverse Event of Special Interest

The term Adverse Event of Special Interest (AESI) relates to any specific AE that has been identified at the project level as being of particular concern for prospective safety monitoring and safety assessment within this study, e.g. the potential for AEs based on knowledge from other compounds in the same class.

The following are considered as AESIs:

Liver injury

- An elevation of AST and/or ALT \ge 3-fold ULN and INR \ge 1.5-fold ULN measured at the same visit, or in samples drawn within 30 days of each other, OR
- An isolated elevation of AST and/or ALT ≥ 5-fold ULN

Ketoacidosis (KA) in diabetic and non-diabetic population

If metabolic acidosis, KA and DKA is suspected, further investigations should be done according to the medical judgment and the clinical course until a diagnosis is made and/or the patient is recovered.

Due to its mechanism of action, empagliflozin may potentially modify the clinical presentation of KA which may occur at lower plasma glucose levels in patients with DM and potentially also in non-diabetic patient population. The diagnosis of KA in these patients can be based on arterial pH \leq 7.30, serum bicarbonate levels <15 mmol/L and measurement of serum beta-hydroxybutyrate levels. Other diagnostic criteria which can support the diagnosis of KA are urine ketones and anion gap >10 mmol/L.

Investigators should note that not all criteria mentioned above need to apply for the diagnosis of KA, and clinical judgment should also be taken into consideration.

Lower limb amputation

Any event leading to a lower limb procedure of amputation, auto-amputation or disarticulation as defined below is considered as an AESI.

"Amputation is a resection of a limb through a bone. Disarticulation is a resection of a limb through a joint. Auto-amputation is a spontaneous separation of non-viable portion of the lower limb.

Not included in this definition are debridement (removal of callus or dead tissue), procedures on a stump (like stump revision, drainage of an abscess, wound revision etc.) and

ONIS New Data Collection Protocol

Document number: c42645766-03

Page 29 of 54

Study number: 1245-0323

Proprietary confidential information © 2024 Boehringer Ingelheim International GmbH or one or more of its affiliated companies

other procedures (e.g., nail resection or removal) without a concomitant resection of a limb (amputation or disarticulation)." (International Working Group of Diabetic Foot, 2015). Each lower limb amputation, disarticulation, or auto-amputation should be reported separately. The SAE report should include the date of the procedure, the level of amputation or disarticulation, the medical condition(s) leading to the procedure and if the patient had some of the known risk factor(s) for lower limb amputation.

Specific Adverse Event

The following are considered as specific adverse events:

Severe hypoglycaemia (defined as low blood sugar causing severe cognitive impairment which requires assistance from another person for recovery), Urinary tract infection, Genital infection (see below for definition), Bone fracture, Urinary tract malignancy, Volume depletion (defined as whether or not a participant has experienced symptoms they attribute to dehydration, such as feeling faint or fainting), Acute kidney injury (see below for definition), Gout, Hyperkalaemia

Definitions:

Acute Kidney injury (AKI):

Confirmation of acute kidney injury requires evidence of one of the following:

- i. An increase in serum creatinine to 1.5-times a recent historical value (which is presumed to have increased within about a week); OR
- ii. Initiation of Renal Replacement Therapy for acute kidney injury

Note: Adapted from 2012 KDIGO staging guidance. Increase in serum creatinine of \geq 27 μ mol/L (or ≥0.3 mg/dL) within about 48 hours has been excluded from the definition of AKI stage 1 as this is likely to occur simply due to natural variation in these participants with advanced CKD. Similarly, serum creatinine \geq 353.6 µmol/L (or \geq 4.0mg/dl) has been excluded from the definition of AKI stage 3 as this may be less than their recent historical measurement.

Genital infections including Fournier's gangrene:

- i. A genital infection is any bacterial or fungal infection of the genitals or perineum, including vulvovaginitis, balanitis and infections of skin between the genital and
- ii. Necrotising fasciitis of the perineum is a subset of all serious genital infections characterized by fulminant tissue destruction which may extend from a cellulitis to include fasciitis and myositis. In men, in which it is more common, it can affect the scrotum and penis. In both sexes, it can rapidly spread to involve the anterior abdominal wall and gluteal muscles.
- iii. Necrotising fasciitis of the perineum is characterised by:

ONIS New Data Collection Protocol

Page 30 of 54

Study number: 1245-0323 Document number: c42645766-03

Proprietary confidential information © 2024 Boehringer Ingelheim International GmbH or one or more of its affiliated companies

- a. Perineal inflammation (erythema and oedema) with or without evidence of necrosis, severe pain (out of proportion to examination findings), and crepitus or bullous changes (indicating gas gangrene, evident in perhaps a half of cases);
- b. Systemic features of infection;
- c. A need for rapid surgical debridement and intravenous antibiotics; and
- d. Histopathological evidence of extensive tissue destruction, inflammation with abundant bacteria along fascial planes and sometimes necrotising myositis.

Note: Necrotising fasciitis of the lower limb and infections developing from primary ano-rectal disease are not considered a serious genital infection.

ONIS New Data Collection Protocol

Page 31 of 54

Study number: 1245-0323 Document number: c42645766-03

Proprietary confidential information © 2024 Boehringer Ingelheim International GmbH or one or more of its affiliated companies

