9.2.3.2 Visit 2 (Follow-up 1: 12 weeks from Visit 1)

After 12 weeks from Visit 1, the participant returns for follow-up. The following data will be collected:

- Visit date
- Physical examination information (weight, BMI, blood pressure)
- Concomitant medication use
- Any changes in the JARDIANCE administration status
- Efficacy assessment: UACR (The measurement taken on the date closest to the visit date is collected.)
- Any changes in the laboratory test results (HbA1c, eGFR, serum creatinine, etc.: if available) if there is any lab result which was clinically significant compared to data before JARDIANCE® treatment
- Safety assessment: any AEs noted
- Study completion status (if applicable)
- Investigator's overall efficacy assessment (if applicable)

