9.3.2 Outcomes

9.3.2.1 Primary outcomes

The primary outcomes are the safety outcomes calculated as the incidence of:

- AEs
- Serious adverse event (SAEs)
- Non-serious adverse events
- Adverse drug reaction (ADR)s
- Serious adverse drug reactions
- Unexpected adverse events
- Adverse events of special interest (AESIs)
- Specific adverse events
- Adverse events leading to temporary or permanent discontinuation
- Adverse events by intensity
- Adverse events by outcome of the events
- Adverse events by causality
- Adverse events leading to death

Assessment of safety:

- Adverse events (event name/ symptoms/ sign)
- Onset date, End date
- Intensity (Mild/ Moderate/ Severe)
- Serious (Serious/ Non-Serious)
- Outcome of the event (Recovered/ Not yet recovered/ Sequela/ Fatal/ Unknown)
- Causality (Certain/ Probable·Likely/ Possible/ Unlikely/ Conditional· Unclassified/ Unassessable·Unclassifiable)
- Action taken with study drug due to AE (Dose not changed/ Dose reduced/ Dose increased/ Drug withdrawn/ Not applicable)

ONIS New Data Collection Protocol

Page 19 of 54

Study number: 1245-0323 Document number: c42645766-03

Proprietary confidential information © 2024 Boehringer Ingelheim International GmbH or one or more of its affiliated companies

- Adverse events of special interest (Liver injury, Ketoacidosis in diabetic and nondiabetic population, Lower limb amputation)
- Specific adverse events (Severe hypoglycaemia, Urinary tract infection, Genital infection, Bone fracture, Urinary tract malignancy, Volume depletion, Acute kidney injury, Gout, Hyperkalaemia)

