9.4 DATA SOURCES

The source data will be captured from the medical records of the patients who have consented to data release. Details on how to capture the data are described in section 9.10.2.

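### Volume depletion, part of a primary outcome, is defined only by the participant's own attribution of symptoms, so the specific-adverse-event count can miss investigator-diagnosed cases and include undiagnosed ones

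*Protocol*

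**What the plan says.** Protocol section 9.3.2.1 introduces its list with "The primary outcomes are the safety outcomes calculated as the incidence of". Specific adverse events are one of the 13 entries that follow. The same section names their members, beginning "Specific adverse events (Severe hypoglycaemia, Urinary tract infection, Genital infection, Bone fracture, Urinary tract malignancy, Volume depletion", and then acute kidney injury, gout and hyperkalaemia. It gives names only.

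The definition stands in section 11.1: "Volume depletion (defined as whether or not a participant has experienced symptoms they attribute to dehydration, such as feeling faint or fainting". Neither that section nor any other adds a physical sign, blood pressure or laboratory criterion, or an investigator's diagnosis.

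On data, section 9.4 says: "The source data will be captured from the medical records of the patients who have consented to data release". Section 9.10.2.1 requires all eCRF data to come from source documents. The safety item at the 12-week visit is "Safety assessment: any AEs noted", and the 24-week visit repeats it.

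The general definition of an adverse event in section 11.1 is wide: "An AE can therefore be any unfavorable and unintended sign (e.g. an abnormal laboratory finding), symptom, or disease".

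**The concern.** The definition reads like a yes/no interview question, with the participant as assessor of both the symptom and its cause. The study lists no such question. Whether the deciding fact reaches the record depends on what each of about 20 sites happens to ask or write down.

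The wording also differs from the rest of its list. For acute kidney injury, section 11.1 says "Confirmation of acute kidney injury requires evidence of one of the following", and then gives a creatinine rise or the start of renal replacement therapy. Genital infection is defined as an infection. Specific events with no definition, such as gout or bone fracture, fall back on the investigator's ordinary diagnosis. Only volume depletion turns on the participant's opinion about cause, and the stated rule displaces the investigator's diagnosis.

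At stake is the count in a named primary-outcome category, in a study whose primary objective is safety. The amendment table in section 5 shows that the specific-event list followed a regulator's review comment, and that the definitions were added later to make the terms clear.

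**Working it through.** The protocol gives no expected rate, sensitivity or specificity for volume depletion, so there is no figure to reproduce. The check sets the stated rule beside the data that the study collects.

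**Step 1: what the rule needs.** It needs (a) a symptom and (b) the participant's belief that dehydration caused it. A diagnosis is neither necessary nor sufficient.

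**Step 2: what is collected.** The visit lists in section 9.2.3 and the flow chart in section 9.2.5 hold adverse events but no item for (b). The adverse event form in Annex 4 asks for an event term, with the diagnosis if available, and for the investigator's view on causality. It has free text in which a participant's belief could be written, but no field for it. The eCRF page is not shown.

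**Step 3: the four possible cases.**

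| Investigator diagnoses volume depletion | Participant-attributed symptom recorded | Counted under section 11.1 | Counted if diagnosis decides |
|---|---|---|---|
| Yes | Yes | Yes | Yes |
| Yes | No | No | Yes |
| No | Yes | Yes | No |
| No | No | No | No |

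The two rules disagree only in the second and third rows.

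**Step 4: size.** Let b be the number of participants in the second row, c the number in the third, and N the safety set. The net error in incidence is (c − b)/N. The protocol gives neither b nor c. With 250 participants planned, N is at most 250, so one misclassified participant moves the incidence by at least 1/250 = 0.4 percentage points. If b and c happen to be equal, the incidence is unchanged but the wrong participants are counted.

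**Step 5: where else these events appear.** Section 11.2 collects all serious and non-serious adverse events. Section 9.7.2 codes them in MedDRA and tabulates them by system organ class and preferred term. An event in the second row is therefore still reported under its own term and, if serious, among the serious adverse events.

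**The case against.** The best defence is that nothing is lost. Any sign, laboratory finding, symptom or disease is an adverse event, all are collected and coded, and the overall and serious categories are themselves primary outcomes. This stands, and it limits the point to one category. It does not make that category's count right.

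A reader might infer that investigator-diagnosed volume depletion is never counted. The wording does not support that: a diagnosed case with a recorded symptom that the participant blames on dehydration is counted.

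A reader might also infer that participants' reports have no route into the data. They do. Section 9.2.3.1 asks participants to contact the investigator about adverse events, section 11.2 requires detailed records of all such events, and section 9.9.1 seeks information from those lost to follow-up. What is missing from the listed items is narrower: the participant's belief about cause.

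The contrast with the other specific events should not be pressed too far. Severe hypoglycaemia has no glucose threshold, and genital infection needs no laboratory confirmation. A symptom-based definition is not odd in itself. The oddity is that the participant's attribution alone decides.

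Finally, the list of preferred terms can properly be left to the statistical analysis plan. The case rule cannot, because the protocol already fixes one, and a plan based on investigator diagnosis would contradict section 11.1.

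**Conclusion.** The point holds in a limited form. Section 11.1 states a rule that can misclassify in both directions within the specific-adverse-event category, and that rests on a fact the study does not list for collection. The general and serious adverse event tables are unaffected. Neither the size nor the net direction of the error can be derived from the protocol, so no claim is made that the incidence will be too high or too low. The conclusion assumes that the definition is applied as written. If sites instead use their own judgement, the count will mix different rules, which is also a reason to amend the text. The change is worth making, because a component of a primary outcome is affected and the repair is small.

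**What to change.** Amend section 11.1 so that volume depletion counts any adverse event that the investigator reports as volume depletion, for example dehydration or hypovolaemia, whether or not the participant attributes symptoms to dehydration. Tabulate events that rest only on participant-attributed symptoms in a separate supportive row. Leave the preferred-term list to the statistical analysis plan. Terms such as orthostatic hypotension need care there, because counting all of them would bring in cases with other causes.

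The cost is a wording change, a term list and one extra table row, with no added visits or tests. The small loss is direct comparability with any count based on the self-report wording, which the supportive row largely preserves.
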